10.1 Adverse Events

All adverse events (AEs) will be collected from the time of informed consent through 14 days after the last dose of study medication. All AEs will be classified by SOC and PT using MedDRA Version 18.0 and presented in subject listings.

AEs that occurred from the first dose of study medication up to 14 days after the last dose will be considered treatment-emergent AEs (TEAEs). Only TEAEs will be counted in the summary tables described below. If more than one AEs that map to the same SOC or the same PT are occurred in a subject, the subject will be counted only once at each level of summarization (i.e., SOC level or PT level) using AE with the strongest outcome and/or severity.

If partial dates of onset are missing, the following imputation algorithm will be applied;

- If the information of period of onset is 'After first dose of study drug' and the month of onset is same as the first dosing date but day is unknown, the day will be same as the first dosing date.
- If the information of period of onset is 'After first dose of study drug' and the month of onset is different from the first dosing date but day is unknown, the day will be first day of the month.

All AEs will be listed. TEAEs will be summarized as assessments of short term safety and long term safety, separately. For assessment of short term safety, following TEAEs will be included;

- if a subject takes study medication for more than 12 weeks (beyond Visit 5), AEs that occurred until Visit 5 will be summarized;
- if a subject takes study medication for 12 weeks or less than 12 weeks, all TEAEs will be summarized.

For assessment of long term safety, the target safety population will be limited to subjects who continue to Part B in two previous protocols (original protocol:06Oct2012 and protocol amendment 1: 11Mar2016) and take study drugs more than 12 weeks (beyond Visit 5) and TEAEs after 12 weeks (beyond Visit 5) will be summarized.

The following summary tables of TEAEs will be produced:

1) Overview of Adverse Events

For each treatment group, the number of events and subjects who experience

- TEAEs
- Serious TEAEs
- TEAEs leading to withdrawal
- TEAEs with an outcome of deaths

will be counted and the incidence proportion will be calculated for each treatment group. The difference in the incidence proportion and its 95% confidence interval (CI) will also be calculated. Treatment-related AEs will be summarized by the same category as TEAEs, except for death.

2) Summary of TEAEs and Treatment-related AEs by System Organ Class and Preferred Term

For each treatment group, the number and percentage of subjects who experience TEAE (and Treatment-related AEs) will be counted by SOC and PT for assessments of short and long term safety. The difference in the percentage and its 95% CI will also be calculated. For assessment of short term safety, This analysis will be performed for specific TEAEs for assessment of short term safety, namely

- Breast-related TEAE
- Reproductive system-related TEAE
- Lipid-related TEAE
- Coagulation-related TEAE
- Chemistry-related TEAE

TEAEs and Treatment-related AEs at least 2% in any treatment groups will be analyzed in a similar way.

3) Summary of Serious TEAEs and TEAEs Leading to Withdrawal by System Organ Class and Preferred Term

For each treatment group, the number and percentage of subjects who experience serious TEAE and TEAE leading to withdrawal will be counted by SOC and PT for assessment of short term safety. The difference in the percentage and its 95% CI will also be calculated.

4) Summary of TEAEs and Treatment-related AEs by System Organ Class by Maximum Severity and Outcome

For each treatment group, the number and percentage of subjects who experience TEAE (and treatment-related AEs) will be counted by SOC and PT, and by maximum

severity and outcome for assessment of short term safety. The order of severity and outcome are shown in Table 6.

Table 6 Order of Priority for Counting Number of Subjects

Order of Priority	Severity	Outcome
1	Severe	Fatal
2	Moderate	Recovered/Resolved with sequelae
3	Mild	Not recovered/Not resolved
4		Recovering/Resolving
5		Recovered/Resolved
6		Unknown

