| Sponsor Contact: | PPO Shionogi Inc. [name] TEL: PPO FAX: PPO |

Issue Date:

| | |
|-----------------------------|------------------|
| Original (Version 1) | 06 October 2015 |
| Version 2 | 11 March 2016 |
| Version 3 | 02 November 2016 |

Confidentiality Statement

This document and the information contained herein or attached hereto (“Confidential Material”) are confidential and proprietary to Shionogi Inc. This Confidential Material should only be viewed by those individuals or companies that have been given prior written authorization to do so by Shionogi Inc. (“Authorized Users”). This Confidential Material should not be made available in any form to any person or company, other than the Authorized Users and their respective employees or associates on a need-to-know basis, without the written consent from Shionogi Inc.

SYNOPSIS

Study Title:

A Phase 3, Randomized, Double-blind, Placebo-controlled Multicenter Study to Evaluate the Efficacy and Safety of Ospemifene in Patients with Moderate to Severe Vaginal Dryness, a Symptom of Vulvo-vaginal Atrophy (VVA) due to Menopause.

Study Number:

1517I0231

Study Phase: 3

Objective

The objective of this study is to evaluate the efficacy and safety of ospemifene 60 mg once daily (QD) compared with placebo in treatment of vulvo-vaginal atrophy (VVA) due to menopause in women with moderate to severe vaginal dryness as the most bothersome symptom (MBS) of VVA.

Study Design:

This is a multicenter, randomized, double-blind, placebo-controlled study to assess the efficacy and safety of ospemifene 60 mg QD in postmenopausal women with vaginal dryness as the MBS of VVA due to menopause.

The study was previously designed as a two part study; Part A (12 week efficacy and safety assessment period) and Part B (long term, 92 week safety assessment period, beginning at week 12 and ending at week 104). The current version of the protocol has been amended to remove Part B based on enrollment challenges and site feedback. Data will be handled as described in the Note at the end of the Synopsis.

This study consists of 3 periods: a Screening Period of up to 4 weeks during which eligibility will be assessed; a Treatment Period of 12 weeks during which efficacy and safety will be assessed, and a Follow-up Period of 2 weeks after the last dose of study medication.

Study Population:

Approximately 600 subjects will be randomized to this study.

Eligibility Criteria

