For percentage of parabasal cells, percentage of superficial cells and vaginal pH, a Mixed-effects Model Repeated Measures (MMRM) approach will be used. In the model, repeated measurements of the change from baseline at Week 4, Week 8 and Week 12 will be the response variable. Baseline value and study center may be modeled as covariates. Superiority of ospemifene to placebo will be evaluated by

testing the mean difference between the two treatment groups at Week 12.

For dryness as the MBS, Generalized Estimating Equations (GEE) model will be used to fit a marginal proportional odds model to the longitudinal ordered categorical data (Fitzmaurice et al., 2011). In the model, repeated measurements of the change from baseline in dryness at Week 4, Week 8 and Week 12 will be the response variable.

Baseline severity of dryness and study center may be modeled as covariates.

Superiority of ospemifene to placebo will be evaluated by comparing the two treatment groups at Week 12.

Safety

The number and percentage of subjects who experience treatment-emergent adverse events (TEAEs) will be summarized by treatment group, and during Treatment Period and Follow-up period separately. Serious adverse events (SAEs) and AEs leading to discontinuation will be tabulated in a similar manner. Details will be described in the Statistical Analysis Plan (SAP).

Study Duration:

Subjects may be participating in the study for up to 18 weeks.

Date of Original Version: 06 October 2015

Date of Version 2: 11 March 2016

Date of Latest Amendment: 02 November 2016

NOTE:

For subjects consented under Protocol version 11 March 2016:

- Dual-Energy X-ray Absorptiometry (DXA) Scan
Bone mineral density (BMD) was determined using DXA scans. Images of the hip and lumbar spine were sent to a central reader. The date of imaging was entered in the eCRF. Detailed procedures are specified in a separate document. Details about the central BMD laboratory are provided in Section 10.1.
- Standard mammogram scans used to determine Breast Density .

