2. STUDY OBJECTIVES

2.1 Primary Objectives

Objective 1: To assess the efficacy of ospemifene 60 mg daily at 12 weeks of treatment, relative to placebo, in the treatment of vaginal dryness, a symptom of vulvar and vaginal atrophy, due to menopause.

Hypothesis: After 12 weeks of treatment, ospemifene 60 mg QD, relative to placebo, significantly improves all 4 co-primary efficacy endpoints:

- Percentage of parabasal cells in the maturation index of the vaginal smear
- Percentage of superficial cells in the maturation index of the vaginal smear
- Vaginal pH
- Severity of self-reported MBS of vaginal dryness

Objective 2: To assess the safety and tolerability of ospemifene 60 mg QD during 12 weeks of treatment, relative to placebo.

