13 CHANGES FROM PROTOCOL

13.1 Safety Analysis

- Calculation of the CI of the incidence proportion for each treatment group was planned using the Clopper-Pearson method in the Section 9.11.1. It was replaced with the CIs for the difference between treatments because these are more informative.

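### The SAP's short-term adverse event summary mixes on-drug and off-drug time over unequal windows, and drops without declaration the protocol Synopsis's separate Treatment and Follow-up summaries

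*SAP*

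**What the plan says.** **Protocol.** The Synopsis (Statistical Methods, Safety) says that subjects with TEAEs "will be summarized by treatment group, and during Treatment Period and Follow-up period separately", with SAEs and AEs leading to discontinuation handled likewise. It describes the first of these periods as "a Treatment Period of 12 weeks during which efficacy and safety will be assessed"; the second is the two weeks that follow the final dose. Primary Objective 2 (Section 2.1, repeated in SAP 3.1) is "To assess the safety and tolerability of ospemifene 60 mg QD during 12 weeks of treatment, relative to placebo". Section 9.11.1, the body text on AE analysis, does not mention the period split. Section 9.1 requires the SAP to specify any deviation from the protocol's analyses and give the reason.

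**SAP.** Section 10.1 counts an event as treatment-emergent from first dose to 14 days after last dose. It then divides the summaries into short term and long term only. For the short-term tables there are two rules:

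- The first covers women who continued: "if a subject takes study medication for more than 12 weeks (beyond Visit 5), AEs that occurred until Visit 5 will be summarized". It leaves out everything later than that visit.
- The second covers women who did not continue: "if a subject takes study medication for 12 weeks or less than 12 weeks, all TEAEs will be summarized". It takes in their off-drug days.

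The long-term tables take TEAEs after Visit 5 in women who went on into the former Part B. None of the table types listed in 10.1 isolates the follow-up period. Section 13.1 declares one safety change, the replacement of Clopper-Pearson intervals: "It was replaced with the CIs for the difference between treatments because these are more informative". It says nothing about periods.

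**The concern.** One proportion per arm, with its risk difference and confidence interval, is computed from two observation windows. Women who stop at or before Week 12 contribute their time on drug plus up to 14 days off it. Women who continue contribute time to Visit 5 only, and any off-drug events they have later fall into the long-term tables. The short-term table therefore does not give incidence during 12 weeks of treatment, which is what Objective 2 asks for. The planned summary tables also do not show which events began after stopping.

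The AE window differs from the SAP's other safety cut-offs too. Exposure (SAP 8.2) ends at last dose for early withdrawals and at Visit 5 for everyone else, and the laboratory-limit analysis (SAP 10.3) uses data until Visit 5. The AE tables thus count up to 14 days of events that lie outside the exposure period reported beside them.

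Finally, the short-term rule treats dosing for more than 12 weeks and dosing beyond Visit 5 as the same thing. They are not, so some women's follow-up events have no clear place.

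**Working it through.** **1. The plan's own time figure.** Screening up to 4 weeks + treatment 12 weeks + follow-up 2 weeks = 18 weeks, which matches Protocol 3.3.1. The period lengths are consistent.

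**2. Observation windows under SAP 10.1.**

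| Woman | Short-term window | Off drug |
|---|---|---|
| Last dose Day 28 | 28 + 14 = 42 days | 14/42 = 33% |
| Last dose Day 56 | 56 + 14 = 70 days | 14/70 = 20% |
| Completes 12 weeks and stops | 84 + 14 = 98 days | 14/98 = 14.3% |
| Continues past Visit 5 | about 84 days | 0 |

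Completer against continuer: 98/84 = 1.167, or 16.7% more time. The 84 days are nominal, because SAP Table 1 gives Visit 5 a target of Day 85 and a window of Day 72 to Day 99.

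**3. Effect on a completer's incidence.** The documents give no AE rates, so the 12-week incidence *I* is an assumption, shown over a range. With the same constant hazard on and off drug, the 98-day incidence is 1 − (1 − *I*)^(98/84).

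| Assumed 12-week incidence | 98-day incidence | Increase (points) |
|---|---|---|
| 10% | 11.57% | 1.57 |
| 20% | 22.92% | 2.92 |
| 30% | 34.04% | 4.04 |
| 40% | 44.90% | 4.90 |
| 50% | 55.46% | 5.46 |

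For a preferred term at the SAP's 2% reporting threshold, 1 − 0.98^(98/84) = 2.3%, an increase of 0.3 points.

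**4. Effect on the between-arm difference when there is no drug effect.** Leaving early stoppers aside, if a share *c* of an arm continues, that arm's incidence is *I* + (1 − *c*)(*I*₉₈ − *I*). The spurious risk difference is the arm difference in *c* times (*I*₉₈ − *I*). Shares continuing are not in the documents. With assumed arm differences of 5 to 20 points and *I* of 20% to 40%:

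- smallest: 0.05 × 2.92 = 0.15 points
- largest: 0.20 × 4.90 = 0.98 points

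If the share continuing is the same in both arms, this is zero.

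**5. Direction of the effect on a true difference (completers in both arms).**

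- Same hazard off drug as on drug: 50% vs 40% (10.0 points) becomes 55.5% vs 44.9% (10.6 points). The difference widens.
- Off-drug hazard equal to placebo in both arms: with placebo at 20%, the event-free fraction over 14 days is 0.80^(14/84) = 0.9635. Then 30% vs 20% becomes 1 − 0.70 × 0.9635 = 32.6% vs 1 − 0.80 × 0.9635 = 22.9%, a difference of 9.6 points (ratio 1.50 to 1.42). The difference shrinks slightly.

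The sign depends on an assumption that the documents do not settle.

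**6. The classification rule.** SAP Table 9 has a category of 85 or more days of exposure within Week 12. A woman dosed for 85 days who stops at a Visit 5 inside its window has taken drug for more than 12 weeks but not beyond Visit 5. The first short-term rule's two conditions disagree for her, and her 14 days of follow-up are not clearly assigned.

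**The case against.** The strongest reply is that the SAP follows the protocol's body. The instruction to separate the periods is in the Synopsis only, in a paragraph that defers details to the SAP. Protocol 9.11.1 plans one TEAE summary per arm and refers to the TEAE definition in 7.6.11.10, which has no end date. AEs are collected through the follow-up call (7.6.11.2). A window to 14 days after last dose matches that collection period and catches reactions that start just after stopping. Cutting continuers at Visit 5 keeps Part B events out of the short-term table. The rule is the same in both arms. A Treatment Period table would still give unequal time, since a woman stopping at Day 28 contributes 28 days.

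Much of this stands. The 14-day window is defensible as a summary, and which table is called primary is a preference. But 9.11.1 is silent on the split rather than against it, and leaving details to the SAP is not the same as removing the split without saying so. Section 13 records another change to the same AE analysis, so this one belonged there as well.

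Three stronger readings are tempting and are not supported:

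- **That pooling dilutes drug effects.** Under a constant hazard it widens the difference; under a placebo-level hazard off drug it narrows it slightly (step 5).
- **That women selected their own window according to tolerability.** The documents do not say that continuing was such a choice. Part B was removed for enrollment challenges and site feedback, so continuing depended at least partly on protocol version and calendar time, which randomization should balance. The earlier protocol versions are not among the documents.
- **That follow-up events cannot be identified at all.** All AEs are listed, onset dates are collected (7.6.11.1), and the table shells are in a separate document. What is missing is a planned summary.

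**Conclusion.** The point holds as a mismatch between documents and a mixed observation window; it does not show a biased comparison. The SAP's short-term TEAE summary covers about 98 days for completers who stop and about 84 for continuers, plans no separate follow-up summary, departs from the Synopsis without declaring it, and does not match the 12 weeks of treatment in Objective 2. The Synopsis and Protocol 9.11.1 also need to be aligned with each other.

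The main effect is on the level: about 1.6 to 5.5 points added to a completer's nominal 12-week incidence, assuming 12-week incidences of 10% to 50% and an equal hazard off drug. This may overstate the effect, because follow-up is a single telephone call without the Visit 5 examinations and laboratory tests. Any spurious between-arm difference requires continuation to differ by arm, and is 0.15 to 0.98 points on the assumed ranges. For comparison, at 300 per arm and 40% to 50% incidence the 95% interval half-width is about 1.96 × √(2 × 0.24/300) = 7.8 to 1.96 × √(2 × 0.25/300) = 8.0 points. The change is worth making because it costs little and answers the stated objective, not because the comparison is seriously at risk.

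**What to change.** In SAP 10.1:

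1. Add a Treatment Period table: onset from first dose to the earlier of last dose and Visit 5, for all women, with risk differences and confidence intervals. This matches Objective 2 and the cut-offs in SAP 8.2 and 10.3.
2. Add a Follow-up table: onset in the 14 days after last dose, with women who stopped at or before Visit 5 as the denominator.
3. Keep the pooled table, first dose to 14 days after last dose, alongside.
4. Define continuation past Visit 5 by one criterion instead of equating it with more than 12 weeks of dosing. SAP 8.3 uses the same pairing for concomitant medication and should follow the same definition.
5. Declare and justify any remaining departure in Section 13, and align the protocol Synopsis with 9.11.1.

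No new data are needed. The cost is SAP wording and one or two more tables. There will be fewer events in the Treatment Period table, and reactions that start just after stopping must be read from the follow-up or pooled table.

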10 SAFETY

Safety analyses will be conducted on the Safety Population. For all safety analyses, emphasis will be on characterizing the changes from baseline and flagging clinically relevant abnormal findings, if feasible. If a test or assessment is measured more than once prior to the first dose of study medication, the baseline measurement is the last non-missing value that is observed prior to the first dose of study medication.

To calculate 95% confidence intervals for differences in incidence proportions, FREQ procedure and RISKDIFF option will be used.

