12 PROGRAMMING CONVENTIONS

Unless otherwise stated, tables, figures, and listings (TFLs) will be made in accordance with the following specifications on programming:

1) Display digit of various statistics

The display digit of various tests (such as laboratory tests) is as specified for each respective test, in principle. Display digit of statistics for efficacy and safety analyses are defined in Table 8.

Table 8 Display Digit of Statistics for Efficacy and Safety

Statistics		Display Digit
Efficacy and Safety	The number of subjects	Displayed as integer
	Mean, median, 95% confidence interval	One more decimal place than raw data
	Standard deviation, standard error	One more decimal place than raw data
	Maximum, minimum	Same number of decimal places as raw data
	Percentage (%)	Round off to one decimal place
	p-value	Round off to four decimal places Note: p < 0.0001 is displayed as “< .0001”
VVA symptoms	Mean, median, 95% confidence interval, standard deviation, standard error	Round off to two decimal place

2) Handling of outliers

Possible outliers will not be omitted from the analyses.

3) Categories used in the summarization

Categories used in the summarization of items are shown in Table 9. The breakdown of categories may be changed with blind inspection of distribution as needed.

Table 9 Subject Characteristics and Items of Therapeutic Process

Items	Categories
Age (years)	< 45, >= 45 to < 55, >=55 to < 65, >= 65
BMI (kg/m ²)	< 18.5, >=18.5 to < 25, >=25 to < 30, >=30
Ethnicity	Not Hispanic or Latino, Hispanic or Latino, Not reported, Unknown
Race	American Indian or Alaska Native, Asian, Black or African American, Native Hawaiian or Other Pacific Islander, White, Other
Uterus	Yes, No
Current hot flushes	Yes, No
Previous hormone treatment	None, any hormone treatment, hormone replacement therapy (excluding vaginal), vaginal hormone products
Number of Days of Treatment Exposure within Week 12 (days)	>=1 to <= 7, >=8 to <= 14, >=15 to <= 28, >=29 to <= 42, >=43 to <= 56, >=57 to <= 70, >=71 to <= 84, >= 85
Number of Days of Treatment Exposure after Week 12 (days)	>=1 to <=14, >=15 to <=28, >=29 to <=56, >=57 to <=84, >=85 to <=168, >=169 to <=273, >=274 to <=364, >=365
Medication compliance (%)	< 85, >= 85

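### Adverse events after Visit 5 are compared as crude percentages over follow-up of varying length, with no person-time measure

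*SAP*

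**What the plan says.** The protocol synopsis records that the study once had a Part B of 92 weeks, running from Week 12 to Week 104, and that the protocol was "amended to remove Part B based on enrollment challenges and site feedback". For data after Visit 5, the synopsis note asks only that subjects with TEAEs be summarized by treatment group and leaves the details to the SAP.

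SAP Section 10.1 supplies them. For long-term safety, "the target safety population will be limited to subjects who continue to Part B in two previous protocols" and who took drug beyond Visit 5; for these women, "TEAEs after 12 weeks (beyond Visit 5) will be summarized". Two tables carry the result:

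- The overview, which is not restricted to one period. Events and subjects "will be counted and the incidence proportion will be calculated for each treatment group", with a between-arm difference and 95% CI.
- The table by system organ class and preferred term. Subjects "will be counted by SOC and PT for assessments of short and long term safety", and "The difference in the percentage and its 95% CI will also be calculated".

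The opening of Section 10 fixes the interval method: "FREQ procedure and RISKDIFF option will be used". This is a difference of two proportions and has no person-time term. No exposure-adjusted rate, time-to-event method or exposure stratum appears in Section 10. Section 13.1 replaces the protocol's within-arm Clopper-Pearson intervals with intervals for the difference, so the between-arm contrast carries the only planned interval for these events.

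Two other parts of the SAP bear on the point. Section 8.2 repeats the exposure and compliance summary for the period after Visit 5, with Table 9 giving exposure categories. Section 7.1 summarizes reasons for discontinuation after Visit 5 by arm.

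**The concern.** The short-term tables have a nominal 12-week horizon. The long-term tables have none: each woman's time after Visit 5 depends on when she entered Part B, when it was stopped for her, and whether she left earlier for another reason. A woman followed for two weeks and one followed for many months count equally in the denominator. The resulting percentage is a risk over an unspecified mixture of durations, even if the arms are perfectly balanced.

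The between-arm difference raises a second, conditional issue. The long-term set is selected after randomization, because a woman had to reach Visit 5 and continue. Randomization therefore does not guarantee equal time at risk in the two arms. If time at risk did differ, a crude difference and its interval would mix event rate with duration, and could create a contrast or hide one.

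**Working it through.** **The plan's own figure.** The documents state no expected rate, sample size or precision for long-term adverse events. The only design figure is at least 90% power for the co-primary endpoints with 300 per arm (Protocol 9.2). It reproduces for the limiting endpoint, dryness: Φ(0.27 × √150 − 1.96) = Φ(1.35) = 0.911. The other three are about 1.00. This has no bearing on the safety tables.

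**How long follow-up could be.** The protocol dates the original version 06 October 2015 and the amendment 02 November 2016, which is 393 days. Taking off the 7-day minimum between Visits 1 and 2 and 84 days of treatment gives 393 − 7 − 84 = 302 days as the most a woman could have accrued after Visit 5 by the amendment date. The top Table 9 category (365 days or more) would need at least 365 − 302 = 63 days of dosing past that date. SAP 10.1 gives the original protocol's year as 2012; I used the protocol's own date, and the SAP date should be corrected.

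**No defined horizon.** Assume a constant event rate r per person-year, the same for everyone. Risk over D days is 1 − exp(−r × D / 365.25).

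| Assumed r | 14 days | 168 days | 365 days |
|---|---|---|---|
| 0.3 | 1.1% | 12.9% | 25.9% |
| 0.6 | 2.3% | 24.1% | 45.1% |
| 1.0 | 3.8% | 36.9% | 63.2% |

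Adding the 14-day TEAE window after last dose raises the middle row to 4.5%, 25.8% and 46.3%; the gradient remains.

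**Effect on the difference if exposure were unequal.** Assume the same r in both arms, exposure uniform on 1 to 365 days in one arm, and the same distribution multiplied by f in the other. With a and b the exposure limits in years, the mean crude risk is 1 − [exp(−ra) − exp(−rb)] / [r(b − a)]. At r = 0.6 and f = 1, a = 0.0027 and b = 0.9993, giving 1 − (0.9984 − 0.5490) / 0.5980 = 24.9%. The table shows the spurious difference in percentage points, from unrounded risks.

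| Assumed r | Equal exposure | 10% shorter | 25% shorter | 50% shorter |
|---|---|---|---|---|
| 0.3 | 0.0 | 1.2 | 3.2 | 6.5 |
| 0.6 | 0.0 | 2.1 | 5.3 | 11.2 |
| 1.0 | 0.0 | 2.7 | 7.2 | 15.5 |

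If the upper limit is 302 days instead of 365, the r = 0.6 row becomes 0.0, 1.8, 4.7 and 9.8. The true rate difference is zero in every cell.

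**Effect on the interval.** The simulation used 4,000 trials per setting, r = 0.6 in both arms, exposure uniform on 1 to 365 days, and a simple large-sample 95% interval for the risk difference. With an assumed 100 women per arm, the interval excludes zero in 5% of trials with equal exposure, 14% with exposure 25% shorter in one arm, and 52% with 50% shorter. With 50 per arm the figures are 6%, 10% and 32%; with 150 they are 5%, 19% and 72%.

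**Masking.** Rates of 0.6 and 0.4 per person-year both give a crude 17.6% if the higher-rate arm has two-thirds of the other arm's exposure.

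**The case against.** A reader might infer that exposure after Visit 5 actually runs from one day to over a year. The documents do not support that. The span comes from the Table 9 display categories, which the SAP allows to be changed after blinded inspection. No observed exposure is reported, and at most 302 days were possible by the amendment date.

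A reader might also infer that removing Part B made the arms non-comparable. That does not follow. The removal was administrative, in a blinded trial randomized 1:1, and by itself shortens follow-up in both arms alike; the equal-exposure column above is zero throughout. Distortion needs unequal dropout or unequal entry into Part B, and the documents show neither. They do not exclude them: SAP 7.1 attributes to the amendment only those discontinuations after Visit 5 whose reason was entered as *other*.

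Nor can one say that the crude percentage understates long-term incidence, because the SAP defines no fixed-horizon incidence to compare it with. The current objectives cover 12 weeks, and no hypothesis rests on these tables.

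The SAP also gives partial protection. Exposure and discontinuation reasons after Visit 5 are tabulated by arm, the overview counts events as well as subjects, and all adverse events are listed. An imbalance would be visible. That stands, but seeing an imbalance does not adjust the difference or its interval, and it gives the percentage no horizon.

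**Conclusion.** The point holds in a limited form. The lack of a time horizon follows from the design and needs no assumption about imbalance. Distortion of the between-arm difference is conditional. Under a constant rate of 0.3 to 1.0 per person-year and exposure uniform over a year, it is 1.2 to 2.7 points if one arm's exposure is 10% shorter, 3.2 to 7.2 if 25% shorter and 6.5 to 15.5 if 50% shorter, and zero if exposure is equal. The rates, exposure distributions and numbers per arm are illustrative; the documents give none of them for the long-term set. Primary efficacy and the 12-week safety tables are unaffected. This is a worthwhile, low-cost improvement to how the only planned long-term contrast is reported, and not evidence that the contrast is biased.

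**What to change.** In SAP 10.1, for the long-term tables:

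- Add the number of subjects with an event per 100 patient-years at risk, by arm, with a rate difference and 95% CI. Time at risk runs from Visit 5 to the first event of that type, or to last dose plus 14 days.
- Keep the crude counts and percentages and label them descriptive.
- State that the rates are to be read beside the exposure (8.2) and discontinuation (7.1) summaries for the period after Visit 5.

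The cost is a few lines of SAP text and some programming. Section 8.2 cannot be reused directly, since it counts days correctly dosed and not calendar time at risk. Person-time must be derived for the overview and for each class and term from visit, last-dose and onset dates, all of which are collected. The rate assumes a roughly constant hazard, and it does not correct informative dropout or selection into Part B.
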